8.5 Secondary Statistical Analyses

Binary and categorical endpoints (e.g., adverse events and complications) will be tabulated by intervention group. Time in healthcare will be summarized by group using medians and interquartile ranges, and differences between intervention groups will be summarized using 95% confidence intervals generated from generalized linear regression models appropriate for each type of outcome (e.g., binary, count, continuous, etc.). To examine the sensitivity of adherence to the Med-style Food Pattern on changes in serum biomarkers, we will modify the primary analytic model described for Aim 2 by separately adjusting for a binary indicator of adherence (adherent vs. not) and a graded measure of adherence to intervention. Finally, we will use

mediation analyses to explore the extent to which changes in serum biomarkers over time are mediated through intervention-induced changes in weight and physical activity.

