2.0 Background and Rationale

Diverticulitis is one of the most common gastrointestinal indications for inpatient hospital admission, outpatient clinic and emergency room visits, and colon surgery.^{1, 2} At least 20% of individuals with an initial episode of diverticulitis will have one or more painful and unpredictable recurrences.³ The risk of recurrence increases with each subsequent episode.³ Unfortunately, there is no proven pharmacologic means to decrease the risk of diverticulitis.⁴ Currently, secondary prevention relies on segmental colectomy, which is associated with a ~10% risk of major complications and does not eliminate the possibility of future attacks.⁵⁻⁸ In the face of the enormous burden of recurrent diverticulitis, secondary prevention is a high priority.

Diet and lifestyle factors are modifiable targets for prevention of diverticulitis. Multiple large, prospective cohort studies, including work from our group, have identified low dietary fiber, high red-meat intake, and a Western dietary pattern as risk factors for incident diverticulitis.⁹⁻¹³ Physical inactivity, obesity, smoking, and nonsteroidal anti-inflammatory drug use also increase risk.¹⁴⁻¹⁹ An observational study of 51,000 men examining the joint contribution of multiple modifiable risk factors found a linear relationship between number of low-risk factors and diverticulitis incidence. Adherence to a low-risk profile (<51g/day red meat, >23g/day fiber, 2 hours exercise/week, normal BMI and never smoked) decreased the risk of incident diverticulitis by nearly 75% (RR 0.27, 95% CI 0.15-0.48).²⁰ However, these modifiable risk factors have not been evaluated for secondary prevention. Based on the indirect nature of the evidence, U.S. guidelines conditionally recommend diet and lifestyle changes in individuals with a history of diverticulitis. As part of the Dietary Guidelines for Americans, the USDA developed a Healthy Mediterranean-style Food Pattern²¹ that includes the main dietary components associated with primary prevention of diverticulitis and may be effective for secondary prevention. However, barriers to adherence relating to cost, cultural preferences, and food restrictions need to be addressed to consider it a practical intervention in a clinical setting.

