3.0 Study Aims and Methods

3.1 Study Aims

Aim 1. Conduct a randomized trial (n=75) of the USDA Healthy Med-style Food Pattern intervention versus standardized guidance on fiber intake for patients with diverticulitis to determine feasibility of a larger-scale effectiveness trial focused on long-term clinical outcomes (recurrence and complications). We will examine willingness to randomize and assess adherence to USDA Healthy Med-style Food Pattern.

Aim 2. Explore plasma inflammatory markers in a subset of participants (n=40) (IL-6, IL-1, IL-1 β) and fecal calprotectin as short-term, intermediate inflammatory biomarkers of response to treatment and collect samples for future biomarker study.

The hypotheses underlying the IMPEDE trial include 1) A large-scale trial of the USDA Med-style Food Pattern will be feasible (high rate of patient willingness to be randomized, high rate of adherence to the intervention, improvement in Med-style food pattern scores assessed by a well-characterized food frequency questionnaire (FFQ) [measure of extent of use of the Mediterranean diet], acceptability of study survey burden and follow-up). 2) A USDA Med-style Food Pattern reduces serum and fecal biomarkers of inflammation more than standardized

recommendation to encourage a high-fiber diet. Based on prior studies, we expect reductions in these biomarkers will correlate to lower rates of recurrent diverticulitis.

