8.2 Study Feasibilities Measures

We will assess willingness to randomize as the number of eligible patients that randomized divided by the number of eligible patients (Aim 1). We will provide descriptive statistical summaries of time to complete survey materials, time interacting with the USDA Med-style Food Pattern platform, and changes in estimated weekly meal expenses. These data will be used to inform the future large-scale trial including the number of study sites, recruitment rate/study duration and amount of coordinator effort. The rate of willingness to randomize is unknown but as long as it is at least 20% our study will be successful. We would also want at least 50% of those willing to randomize to be willing to give a blood sample and at least half of those to give stool.

8.3 Treatment Fidelity and Adherence:

The Fred Hutch FFQ is a standard method of dietary intake assessment that has been used in several large-scale cohort studies including the Women’s Health initiative.^{153, 154} The degree of adherence with the USDA Healthy Med-style Food Pattern (Aim 1) will be ascertained by assigning point scores based on the estimated daily amounts of the recommended food groups and subgroups habitually consumed. Full points will be awarded to diets that meet all the

recommendations and partial points to diets that do not. Given that the USDA Healthy Med-style Food Pattern provides recommended amounts for relevant food groups, the adherence score will be based on food consumption data normalized per 100 kcal, much along the lines of the Healthy Eating Index (HEI). The HEI is a 100-point score that measures adherence to the DGA and is the standard measure of diet quality in the US. This approach represents an advance over the 14-item food frequency MEDAS score, which ranks adherence to the Med-style diet pattern using 3 cutpoints: ≤ 7 , 8–9, or ≥ 10 (maximal adherence).¹⁴⁵ The data derived will help us understand the central tendency and variability in Med-style food pattern scores which is critical for determining the sample size of a future trial. Degree of adherence to the different aspects of the medical management regimen will also be used to define per-protocol analysis and be considered as potential mediators and/or effect modifiers in explanatory regression models

8.4 Signal Assessment for Biomarkers:

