We will use a linear mixed effects regression model to compare IL-6, IL-10, IL-1 β , and fecal calprotectin measures at baseline, 6, and 12 months after randomization between the two groups. We focus our statistical analysis on IL-6 for which there are preliminary data specific to diverticulitis. The linear mixed effects model will be structured as a longitudinal analysis of covariance, allowing for both cross-sectional and longitudinal comparisons of serum biomarkers between intervention groups. From the model, we will estimate the mean difference and 95% confidence interval in time-averaged IL-6 by averaging the time-specific intervention group differences. The longitudinal analysis of covariance model will adjust for intervention (USDA Med-style pattern versus standardized guidance on fiber intake), recruitment site, and baseline IL-6 as fixed effects: $IL6(t) \sim \beta_0 + \beta_1 \cdot Intervention + \beta_2 \cdot Site + \beta_3 \cdot IL6(t=0)$, for $t = 6$ and 12 months. Follow-up time-point specific differences in mean IL-6 between intervention groups will be estimated by a statistical interaction term between time and intervention status in a second model. Finally, experience in other ongoing trials has shown that serum biomarkers are often positively skewed. We will therefore log-transform IL-6 measurements (and all skewed serum biomarkers) throughout all statistical analyses, and exponentiate model coefficients (as appropriate) for interpretation. Sex and gender (if different from sex assigned at birth) will be considered as exploratory variables in assessing the relationship of the diet-behavioral intervention and the primary and secondary outcomes. Analyses of IL-10, IL-1 β , and fecal calprotectin and patient-reported outcomes will mirror the analyses of IL-6, with the primary goal of estimating plausible intervention effect sizes and standard deviations with the goal of informing a larger phase 3 clinical trial. Formal statistical testing will not be conducted and therefore no multiple testing correction will be employed for analyzing multiple serum biomarkers. Sex as a biological variable will be included in an exploratory analysis of all biomarker models. The study of serum and stool biomarkers will also inform the feasibility of performing a biomarker sub-aim within a future phase 3 trial.

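### The adherence models in Section 8.5 leave out baseline diet score, weight and activity, so their adherence coefficient is open to confounding

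*Combined protocol and SAP*

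**What the plan says.** Section 8.5 states the aim of this analysis: "To examine the sensitivity of adherence to the Med-style Food Pattern on changes in serum biomarkers". It modifies the Aim 2 model by "separately adjusting for a binary indicator of adherence (adherent vs. not) and a graded measure of adherence to intervention". The Aim 2 model, in Section 8.4, "will adjust for intervention (USDA Med-style pattern versus standardized guidance on fiber intake), recruitment site, and baseline IL-6 as fixed effects". Section 8.4 also brings in sex, but only in an exploratory analysis.

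Table 2 takes adherence from the FFQ-based Med-style pattern score at baseline, 6 and 12 months, so the follow-up scores arise after randomisation. Section 8.3 says degrees of adherence may "be considered as potential mediators and/or effect modifiers in explanatory regression models".

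Section 2.0 names other influences on the disease: "Physical inactivity, obesity, smoking, and nonsteroidal anti-inflammatory drug use also increase risk". Table 1 schedules the FFQ, self-reported weight and the IPAQ at baseline. None of these baseline values is listed for the adherence models. Section 8.5 uses weight and activity only in a separate analysis of biomarker changes "mediated through intervention-induced changes in weight and physical activity". The weighting and imputation in Section 8.6 deal with missing data.

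**The concern.** The adherence coefficient is the reason for running these models. Randomisation protects the comparison of arms; it does not protect a comparison of adherent with non-adherent people. Someone who scores well at 6 months may have eaten that way for years, weigh less and be more active, and may have lower IL-6 for those reasons. Baseline IL-6 removes part of such a difference but not necessarily all of it. The pilot could then overstate or understate how strongly inflammation follows diet change, although the data to reduce that problem are already being collected.

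**Working it through.** Section 8.5 gives no effect size, power or sample size, so there is no plan figure to reproduce. The check is of structure, followed by an illustration on assumed inputs.

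**1. The bias term.** The adherence coefficient equals the true effect plus

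bias = cov(adherence, omitted shared-cause part of the outcome) / var(adherence), both given arm, site and baseline biomarker.

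Simple case: graded adherence in within-arm SD units, with a shared cause that raises adherence by u and lowers the log biomarker by u, and that does not act on the baseline biomarker. Then bias = -u². For u = 0.3 this is -0.09; for u = 0.5 it is -0.25. Large-sample simulation (2,000,000 per scenario) agreed. With no true effect the coefficient was -0.09 or -0.25; with a true -0.30 it was -0.39 or -0.55. Adding the shared cause to the model restored 0.00 and -0.30.

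**2. Illustration at the trial's size.**

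- From the documents: up to 40 participants with plasma markers (Section 5.2.1), 2:1 allocation (Section 8.1), and the Section 8.4 terms at 6 and 12 months.
- Assumed: 2:1 carries over to the subset (40 × 2/3 = 26.7, so 27 versus 13); 80% versus 20% adherent; -0.30 log IL-6 if adherent, with all of the arm's effect through adherence; between-person SD 0.35 and within-person SD 0.42; a shared cause correlated 0.5 with the propensity to adhere, acting at -0.25, 0 or +0.25 log per SD; three baseline covariates jointly correlated 0.7 with that cause. The 0.80 in Section 8.7 is a precision example, not a source for the 80%.
- Implied intent-to-treat effect: (0.80 - 0.20) × (-0.30) = -0.18.

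Mean adherence coefficient over 2000 runs per scenario (sampling SD in brackets where available):

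| Shared cause | Misclassified | Section 8.5 as written | Plus three baseline covariates |
|---|---|---|---|
| -0.25 | 0% | -0.443 (0.179) | -0.380 (0.180) |
| 0 | 0% | -0.300 (0.172) | -0.299 (0.177) |
| +0.25 | 0% | -0.154 (0.176) | -0.221 (0.180) |
| -0.25 | 20% | -0.152 | -0.129 |
| 0 | 20% | -0.106 | -0.100 |
| +0.25 | 20% | -0.057 | -0.079 |

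- Share of bias removed, error-free: (0.443 - 0.380) / (0.443 - 0.300) = 0.063 / 0.143 = 44%, and (0.221 - 0.154) / (0.300 - 0.154) = 0.067 / 0.146 = 46%.
- Repeat runs with somewhat different set-ups gave -0.41 / -0.30 / -0.19 and -0.43 / -0.30 / -0.17 for the error-free column, so the pattern is stable.
- Precision cost: the SD rose by 1% to 3% in the table and by 3% to 9% in the repeat runs.
- With 20% misclassified, the covariates shift the coefficient by 0.023, 0.006 and 0.022. A repeat run gave about 0.03 or less, against an SD near 0.15.

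**3. The arm coefficient in the same model.** With complete data,

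adjusted arm = unadjusted arm - (adherence coefficient × arm difference in measured adherence).

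Error-free with no shared cause: -0.18 - (-0.30 × 0.60) = 0.00. With 20% misclassified, the measured proportions are 0.8 × 0.8 + 0.2 × 0.2 = 0.68 and, by symmetry, 0.32, a difference of 0.36. Then -0.183 - (-0.106 × 0.36) = -0.145. The model without adherence gave -0.174 to -0.185 in all six scenarios, close to the true -0.18.

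**The case against.** The strongest reply is that little depends on this. The analysis is secondary, Section 8.4 rules out formal testing, at most 40 people contribute, and no stated decision uses the result. All of that stands.

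The shared causes are also inferred. Section 2.0 lists inactivity and obesity as risk factors for diverticulitis, not as causes of dietary adherence or of IL-6. And the assumed confounding is strong: (0.25 / 0.35)² = 51% of between-person variance if the SD of 0.35 includes it, or 0.0625 / (0.0625 + 0.1225) = 34% if it comes on top. The table therefore shows a mechanism and is not a forecast.

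The gain also shrinks under FFQ error. In two of the three misclassified rows the covariates move the coefficient further from -0.30. One of those moves, from -0.152 to -0.129, does bring it closer to the -0.106 that FFQ error alone produces: there, two opposing biases had partly cancelled. Adjustment addresses confounding and leaves measurement error as it was.

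A reader might infer that the plan will present the adherence-adjusted arm coefficient as the intervention effect, or carry it to phase 3. The documents do not say so. Section 8.4 attaches the aim of "estimating plausible intervention effect sizes and standard deviations with the goal of informing a larger phase 3 clinical trial" to its own analyses, and Section 8.3 already treats adherence as a possible mediator. A reader might also infer that adjustment would reverse the sign of the arm effect. In the error-free run with the -0.25 shared cause the adjusted arm coefficient did average +0.08, but that needs error-free adherence, an effect wholly through adherence and a strong shared cause. The documents supply none of these.

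**Conclusion.** The concern holds in a limited form. As written, the Section 8.5 adherence coefficient is an observational comparison without the obvious baseline covariates, and it can err in either direction. On assumed inputs its mean ran from -0.44 to -0.15 around a true -0.30 with error-free adherence. A sampling SD of about 0.17 to 0.18 leaves any single estimate imprecise in any case. Three baseline covariates removed a little under half of that bias; with 20% misclassified their effect was slight. Neither the size nor the direction can be taken from the documents.

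The arm coefficient in these models is not the total effect, but the plan does not claim that it is, and the Section 8.4 comparison stands.

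A smaller gap lies alongside. Section 8.3 describes a graded FFQ score but gives no cut-off for the binary indicator. The only cut-offs in the documents belong to MEDAS, which Section 4.6 says is not for assessing adherence. Nor is it stated what adherence to the intervention means in the fiber arm. This is a cheap improvement with low stakes.

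**What to change.** In Section 8.5, add baseline Med-style pattern score, baseline weight and baseline IPAQ to both adherence models, and report the adherence coefficient as an observational association. Use baseline values only, because Section 8.5 itself treats later changes in weight and activity as possible mediators.

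As secondary wording, name the FFQ score of Table 2 and Section 8.3 as the adherence measure, give the score cut-off that defines the binary indicator, and say what adherence means in the fiber arm.

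The change is to SAP text; the three variables are already scheduled at baseline. The price is three more covariates in at most 40 participants, with the SD of the adherence coefficient up by roughly 1% to 9% in the runs. Residual confounding remains: smoking and NSAID use, also named in Section 2.0, are not listed by name in Table 1. FFQ error is not corrected.

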8.6 Missing Data

Participants who do not complete some or all of the baseline and follow-up questions will have missing data points. As summarized in the NEJM guidance,¹⁶³ we will employ three primary strategies that are recommended to address missing data. First, the DCC will work in conjunction with the CCC to minimize the amount of missing data since prevention of missing data is preferable to any attempted analysis correction. We will document all reasons for missing data. Second, we will use inverse probability weighting¹⁶⁴ to inflate the weights of cases that are under-represented in the analysis due to selective attrition and/or non-participation. A descriptive analysis that characterizes enrolled participants who do not provide data due to attrition will be conducted, and we will use observed covariates to construct a weighted model using logistic regression. Third, the strategy that we used for two recent primary trial publications^{102, 165} and which we will adopt for our primary analysis is the use of 10-fold multiple imputation to assess the robustness of the results when missing data are imputed and allowing all participants to be included in intent-to-treat analysis. Our primary approach is to use multiple imputation since it provides flexibility in inclusion of relevant baseline and follow-up data. We will also impute missing data under both pessimistic and optimistic scenarios to provide bounds on the statistical uncertainty.

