5.5 Reasons for Withdrawal

Participants may be withdrawn from the study for the following reasons:

1. Participant desires withdrawal (reasons for withdrawal will be recorded); and
2. Study investigator(s) deems it in the participant's best interest to be withdrawn (reason for withdrawal recorded).
3. Participant decides to pursue a different dietary plan that conflicts with study

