5.5.1 Handling of Withdrawals

If the participant requests to be withdrawn from the study, they will be given appropriate treatment, but will not continue with scheduled study follow-ups. If the participant withdraws from the study and withdraws consent for disclosure of future information, no further evaluations will be performed and additional data will not be collected. The investigators may retain and continue to use data collected before withdrawal of consent.

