8.7 Sample Size and Statistical Power

Using 2:1 randomization, we will enroll 50 patients into a USDA Med-style Food Pattern and 25 patients to receive standardized guidance on fiber intake. The analytic aim of this study is to inform potential effect sizes and variance estimates toward the ultimate goal of conducting a definitive phase 3 randomized trial. While 1:1 randomization is more statistically efficient when group variances in outcome are similar, we plan to enroll more participants into the USDA Med-style food pattern intervention to strengthen the precision of estimates of adherence and patient-reported response. Since statistical testing will not be formally conducted, statistical power was not a primary motivation for sizing for this pilot study.¹⁶⁶ However, enrollment of 50 study participants in the USDA Med-style Food Pattern intervention allows a 95% one-sided confidence interval for the intervention adherence rate to exclude rates less than 0.70 if the observed adherence rate is 0.80 or higher in this pilot study.

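### The primary missing-data rule ignores why participants withdrew, so Med-style participants known to have left the diet can be imputed as adherent and the adherence rate is biased upward

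*Combined protocol and SAP*

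**What the plan says.** Table 2 in section 6.1 lists adherence to the Med-style pattern as a primary outcome, scored from the food frequency questionnaire (FFQ) at baseline, 6 and 12 months. Section 8.3 describes a graded point score. Section 8.5 mentions a binary adherence indicator, but no cut-off is given.

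Section 5.5 lists taking up a dietary plan that conflicts with the study as its third reason for withdrawal. Under section 5.5.1, a participant who asks to withdraw "will not continue with scheduled study follow-ups", so later FFQs will be missing.

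Section 8.6 covers participants with incomplete baseline or follow-up questionnaires. It says reasons for missing data will be documented. It then plans inverse probability weighting, ten-fold multiple imputation so that everyone enters the intent-to-treat analysis, and pessimistic and optimistic imputations as bounds. The order of priority is explicit: "Our primary approach is to use multiple imputation since it provides flexibility in inclusion of relevant baseline and follow-up data".

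Section 8.7 says that "enrollment of 50 study participants in the USDA Med-style Food Pattern intervention" permits a "95% one-sided confidence interval for the intervention adherence rate to exclude rates less than 0.70 if the observed adherence rate is 0.80 or higher". The same section also says: "Since statistical testing will not be formally conducted, statistical power was not a primary motivation for sizing for this pilot study".

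**The concern.** For most missing questionnaires, adherence is unknown and imputing it is reasonable. A participant whose recorded reason for leaving is a conflicting diet is different, because the reason itself tells us about adherence after that date. Section 8.6 makes no distinction between the two cases. Nobody who leaves for this reason has a later FFQ, so the data cannot show how the reason relates to later intake, and the imputed value is borrowed mainly from stayers. Inverse probability weighting shares the problem, since it gives more weight to participants who were observed.

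The error has a known direction and grows with the number who abandon the diet. A feasibility trial is meant to reveal exactly that. The adherence estimate would go forward into planning of the larger trial looking better than what the randomized arm achieved.

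**Working it through.** **Inputs.** From section 8.7: 50 participants in the Med-style arm, an observed rate of 0.80, a reference rate of 0.70 and a one-sided 95% limit (z = 1.645). From section 8.6: multiple imputation with m = 10. The documents give no dropout rate and no cut-off for adherent. The withdrawal counts below are therefore assumptions, and a binary definition is taken as given.

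**Step 1: the plan's own figure.** For 40/50, the simple (Wald) lower limit is 0.80 − 1.645 × √(0.80 × 0.20 / 50) = 0.80 − 0.093 = 0.707. This reproduces the statement in section 8.7. It holds for the Wald form; the Wilson limit is 0.693 and the exact limit 0.684. That is a separate matter, and Wald is used below because it matches the plan.

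**Step 2: size of the shift.** Let w participants withdraw because they left the diet, and let x of the n = 50 − w stayers adhere. Imputation without informative predictors centres on q = x/n. Counting the w as not adherent gives x/50 = q × (50 − w)/50. The ratio of the two is (50 − w)/50, so each such withdrawal takes a further 2% of q off the whole-arm rate.

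**Step 3: interval after imputation.** With N = 50 and k = w, an approximation to Rubin's rules is:
- within-imputation variance W = q(1 − q)/N
- between-imputation variance B = (k/N)² × q(1 − q)/n + (k/N²) × q(1 − q)
- total variance T = W + (1 + 1/10) × B
- lower limit = q − t × √T

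For w = 8 and 34/42: q = 0.810, W = 0.00308, B = 0.00059, T = 0.00373, √T = 0.0611 and t = 1.65, so the lower limit is 0.709. The Wald limit on the 42 alone is 0.710.

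| Diet withdrawals (assumed) | Stayers adherent | Imputed rate | Imputed lower limit | Rate over all 50 | Wald lower limit over all 50 |
|---|---|---|---|---|---|
| 5 | 36/45 | 0.800 | 0.701 | 36/50 = 0.72 | 0.616 |
| 8 | 34/42 | 0.810 | 0.709 | 34/50 = 0.68 | 0.571 |
| 10 | 32/40 | 0.800 | 0.694 | 32/50 = 0.64 | 0.528 |

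Of these three, only the row with 8 withdrawals has both an imputed limit above 0.70 and a whole-arm rate below 0.70. With 5 the whole-arm rate is still 0.72. With 10 the imputed limit no longer excludes 0.70.

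**Step 4: long-run behaviour.** In a simulation (20,000 runs per setting), true whole-arm adherence was 0.69 and every withdrawal was a non-adherent diet-leaver. The imputed lower limit exceeded 0.70 in about 14%, 32%, 59% and 86% of trials at 5%, 10%, 15% and 20% withdrawal. With diet-leavers counted as not adherent, the figure was about 6% throughout (Wald limit). These are upper-end values, because the imputation had no informative predictors.

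**Step 5: the denominator in section 8.7.** If only observed FFQs are used, an observed 0.80 gives a Wald limit of 0.702 with 45 FFQs (36/45) but 0.696 with 40 (32/40). The stated property assumes that all 50 contribute.

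**The case against.** The strongest reply is that a reader might infer a test of adherence against 0.70 that the trial could wrongly pass. The documents do not support that reading. Section 8.7 disclaims formal testing and offers 0.80/0.70 as a statement of precision. The numerical feasibility targets in section 8.2 concern willingness to randomize, blood and stool samples, not adherence. This objection stands in full.

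Second, section 8.6 never names adherence, and section 8.7 speaks of an observed rate. That the imputation rule governs adherence is an inference from its reference to the primary analysis, its inclusion of all participants, and Table 2. This also stands. However, the observed-only reading gives the same 34/42 = 0.81, and in either case the plan has no rule for diet-leavers.

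Third, imputation need not rest on stayers alone. A late withdrawal may leave a 6-month FFQ behind, and bi-weekly MEDAS scores and platform use could signal drift away from the diet. Withdrawals unrelated to diet would also dilute the effect. This is fair, and it narrows the gap. But no imputation model is specified, and section 4.6 says MEDAS is not there to assess adherence.

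Fourth, retention is a separate primary outcome, and section 8.6 plans a pessimistic scenario. Heavy loss would therefore be visible. Neither changes the primary adherence estimate, and the pessimistic scenario is undefined and serves only as a bound.

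Finally, a reader might want to count everyone who leaves the online programme as not adherent. The outcome measures food intake, and someone can leave the programme and still eat the pattern, so that extension is not justified.

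**Conclusion.** The point holds as a gap in the analysis rule with a predictable upward bias. It does not show a false pass, because the plan sets no pass mark for adherence. On the assumption that every withdrawal is a diet-leaver and the imputation has no informative predictors, the overstatement is about 0.13 with 8 of 50 withdrawals (0.81 against 0.68) and 0.08 with 5 (0.80 against 0.72). The real gap depends on a dropout rate the documents do not give, and would be smaller with useful predictors or other reasons for leaving. The conclusion also rests on reading section 8.6 as covering adherence and on a binary definition still to be written. It matters because the 0.80/0.70 statement is the plan's only quantitative statement on adherence and presumes a full denominator of 50.

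**What to change.** In sections 8.6 and 8.7:
- Define the primary binary adherence rate over all participants randomized to Med-style, using a prespecified cut-off on the FFQ score.
- At time points after withdrawal, count as not adherent those whose recorded reason is stopping the Med-style diet or adopting a conflicting one. Leaving the online programme alone does not count.
- Impute FFQs that are missing for any other or unknown reason.
- Report the fully imputed and the observed-only rates as sensitivity analyses.
- State that the 0.80/0.70 benchmark refers to this denominator of 50.

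The cost is SAP wording only: sections 5.5 and 8.6 already provide for recording reasons, so no new data are needed. The downside is a somewhat less favourable adherence rate.
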